### **12.6.2.2.3 Sensory Questionnaire**

The sensory questionnaire scores of the individual questions will be summarized by P3P variant (Table 15.2.4.11). The answers to the individual questions along with the scores

#### **Confidentiality Statement**

Data and information contained in this document are considered to constitute trade secrets and confidential commercial information, and the legal protections provided to such trade secrets and confidential information are hereby claimed under the provisions of applicable law. No part of this document may be publicly disclosed without the written consent of Philip Morris Products S.A.

will also be listed (Listing 15.3.4.6). Boxplot of sensory questionnaire scores of the individual questions by P3P variant will be presented (Figure 15.1.4.8).

A mixed model will be conducted for the sensory questionnaire scores with fixed terms for sequence, product variant and two dummy variables for Day 3 and Day 4 (i.e two variables taking value 1 for Day 3 and Day 4 respectively and value 0 for the other study days) and using subject nested within sequence as random effect. In this way Day 1 and Day 2 will be combined to address the multicollinearity as planned in the protocol. The SAS code to be used is shown below:

```
proc mixed data=_data_;  
  class Sequence Product_Variant Day3 Day4 Subject;  
  model SQ_Score = Sequence Product_Variant Day3 Day4 / ddfm=SAT s;  
  random Subject(Sequence) / sub=Subject type=CSH;  
  lsmeans Product_Variant / cl diff alpha=0.05;  
run;
```

In case of model convergence issues, this will be reported in the study report and the variance component (type=VC) covariance structure will be investigated.

Least square means and differences will be presented for the analysis of the sensory questionnaire scores together with 95% confidence interval for the following effects of interest (Table 15.2.4.12):

- P3P 2 vs P3P 3, to describe the effect of an increase of nicotine powder concentration from 2.5% to 5%
- P3P 2 vs P3P 4, to describe the effect of a decrease from 2.25 µm to 1.8 µm of the median particle size in the nicotine powder
- P3P 2 vs P3P 1, to describe the effect of flavor

### **12.6.3 Human Puffing Topography**

Human Puffing Topography parameters per puff and per product use experience will be listed for fixed puffing regimen and *ad libitum* use (Listing 15.3.4.7, Listing 15.3.4.8, Listing 15.3.4.9 and Listing 15.3.4.10).

Human Puffing Topography parameters per puff and per product use experience will be summarized by P3P variant for fixed puffing regimen and *ad libitum* use with geometric mean, CV, arithmetic means, SD and 95% CIs (Table 15.2.4.13, Table 15.2.4.14, Table 15.2.4.15 and Table 15.2.4.16).

### **12.6.4 Weight difference of P3P before and after use**

The values of weight before and after use and their differences will be listed for fixed puffing regimen and *ad libitum* use (Listing 15.3.4.11 and Listing 15.3.4.12) and summarized by P3P variant for fixed puffing regimen and *ad libitum* use (Table 15.2.4.17 and Table 15.2.4.18).

## 12.6.5 Safety Evaluation

Safety variables monitored in this study include: AEs; vital signs (systolic and diastolic blood pressure, pulse rate, respiratory rate); spirometry; ECG data; concomitant medication, clinical chemistry, hematology, urine analysis safety panel, BMI, physical examination, respiratory symptoms (cough assessment).

The primary analysis of Safety parameters will be conducted on the Safety population as described in Section 12.1.3 "Descriptive Statistics".

### 12.6.5.1 Safety Reporting

Safety data will be tabulated on the safety population by exposure period defined as:

- Pre-dose Period: Prior to any Product Use [ICF , first use of P3P 3 test at Day-1[. According to protocol, first use would be P3P 3 product test at Day-1].
- Product Test Period: [First use of P3P 3 test at Day-1, First use of P3P 3 at Day 1[
- P3P 3 Period: [First use of P3P 3 at Day 1, First use of product at Day 2 or time of discharge[
- P3P 1 Period: [First use of P3P 1, First use of the next product variant or time of discharge[
- P3P 2 Period: [First use of P3P 2, First use of the next product variant or time of discharge[
- P3P 4 Period: [First use of P3P 4, First use of the next product variant or time of discharge[
- Safety Follow-Up Period : [from time of discharge, 7 days after discharge].

Safety data will be assigned to the specific safety period where the collection time or start time of the AE is included between beginning and the end of the period.

All AEs occurring from the time of signing of informed consent will be recorded and listed.

Only product emergent AEs will be summarized (the ones occurring during pre-dose period will be listed only). If an AE occurs during the Safety follow up period, then this AE will not be assigned to the last product used but summarized in the Safety Follow-Up Period.

A product emergent AE is defined as an AE that occurs after first P3P product use or that is present prior to first product use and becomes more severe after first product use. All other AEs will not be summarized but provided in listings only.

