Admission, enrolled subjects will perform a product test using up to three P3P 3 products. After the product test, subjects not willing and/or unable to use P3P will be discontinued from the study. Subjects willing to continue their participation in the study after the product test will start their confinement phase.

The Confinement Period (Day -1 to Day 5)

On Day 1, after at least 10 hour abstinence from any tobacco/nicotine containing products, subjects will use P3P 3 during a fixed puffing regimen comprising of 12 puffs in total at a rate of one inhalation every 30 seconds (\pm 5 seconds) in the morning and during an *ad libitum* use period for 60 minutes (\pm 5 minutes) in the afternoon. The start of product use for fixed puffing and for the *ad libitum* use period will be defined as T_0 fix and T_0 ad lib, respectively. There will be a washout period of at least 10 hours between T_0 fix and T_0 ad lib.

A total of 10 blood samples will be taken for fixed puffing PK parameter estimation. One blood sample will be taken prior to the product use (T_0 fix) 15 minutes \pm 5 minutes (T-1). Thereafter in relation to T_0 fix, blood will be drawn at the following time points: T1 after 2 minutes \pm 1 minute, T2 after 4 minutes \pm 1 minute, T3 after 7 minutes \pm 1 minute, T4 after 10 minutes \pm 1 minute, T5 after 15 minutes \pm 2 minutes, T6 after 30 minutes \pm 2 minutes, T7 after 1 hour \pm 5 minutes, T8 after 2 hours \pm 5 minutes, and T9 after 4 hours \pm 5 minutes.

A total of 8 blood samples will be taken for the *ad libitum* PK parameter estimation. One blood sample will be taken prior to product use (T_0 ad lib) at 15 minutes \pm 5 minutes (T-1). In relation to T_0 ad lib, blood will be drawn at the following time points: T1 after 10 minutes \pm 1 minute, T2 after 20 minutes \pm 2 minutes, T3 after 30 minutes \pm 2 minutes, T4 after 40 minutes \pm 5 minutes and T5 after 1 hour \pm 5 minutes, T6 after 2 hours \pm 5 minutes, and T7 after 4 hours \pm 5 minutes.

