On Days 2, 3 and 4, subjects will be instructed to use the assigned P3P variant for the given study day for a fixed puffing regimen in the morning and an *ad libitum* use period in the afternoon as described for Day 1. On each study day including Day 1, start of product use should be at approximately the same time for fixed puffing in the morning and for *ad libitum* use in the afternoon with at least a 10 hour washout period between T_0 fix and T_0 ad lib. There will be a washout of at least 10 hours following T_0 ad lib with respect to the T_0 fix of the morning of the following study day to allow adequate background correction of the nicotine plasma concentrations. The assessments performed on Days 2, 3 and 4 will be the same as those described for Day 1.

On Day 5, there will be no product use, but subjects will remain at the investigational site for additional PK blood sampling for the purposes of estimating the terminal elimination half-life. A total of 5 blood samples will be taken in relation to T_0 ad lib from the last product use at the following time points: T1 after 14 hours \pm 30 minutes, T2 after 16 hours \pm 30 minutes, T3 after 18 hours \pm 30 minutes, T4 after 20 hours \pm 30 minutes and T5 after 24 hours \pm 30 minutes.

Safety measurements including vital signs, ECG, safety laboratory parameters will be performed at several timepoints during the confinement period (Appendix A).

During confinement, the use of any tobacco and nicotine containing products, apart from product use assigned on the assessment days, will not be allowed. Use of tobacco and nicotine containing products will not be restricted once the subjects have left the investigational site.

The Safety Follow-Up Period (from Discharge or Early Termination plus 7 days)

After Discharge on Day 5 or early termination date, the subjects will enter a 7-day Safety Follow-Up Period during which AE/SAEs spontaneously reported by the subjects will be collected.

Any non-serious AE that is ongoing at the time of Discharge or early discontinuation will be followed-up by the Investigator or designee during the Safety Follow-Up Period until it has been resolved, stabilized (i.e., no worsening of the condition), or an acceptable explanation has

Confidentiality Statement

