### **The Confinement Period (Day -1 to Day 5)**

On Day 1, after at least 10 hour abstinence from any tobacco/nicotine containing products, subjects will use P3P 3 during a fixed puffing regimen comprising of 12 puffs in total at a rate of one inhalation every 30 seconds ( $\pm$  5 seconds) in the morning and during an *ad libitum* use period for 60 minutes ( $\pm$  5 minutes) in the afternoon. The start of product use for fixed puffing and for the *ad libitum* use period will be defined as T0 fix and T0 ad lib, respectively. There will be a washout period of at least 10 hours between T0 fix and T0 ad lib.

A total of 10 blood samples will be taken for fixed puffing PK parameter estimation. One blood sample will be taken prior to the product use (T0 fix) 15 minutes  $\pm$  5 minutes (T-1). Thereafter in relation to T0 fix, blood will be drawn at the following time points: T1 after 2 minutes  $\pm$  1 minute, T2 after 4 minutes  $\pm$  1 minute, T3 after 7 minutes  $\pm$  1 minute, T4 after 10 minutes  $\pm$  1 minute, T5 after 15 minutes  $\pm$  2 minutes, T6 after 30 minutes  $\pm$  2 minutes, T7 after 1 hour  $\pm$  5 minutes, T8 after 2 hours  $\pm$  5 minutes, and T9 after 4 hours  $\pm$  5 minutes.

A total of 8 blood samples will be taken for the *ad libitum* PK parameter estimation. One blood sample will be taken prior to product use (T0 ad lib) at 15 minutes  $\pm$  5 minutes (T-1). In relation to T0 ad lib, blood will be drawn at the following time points: T1 after 10 minutes  $\pm$  1 minute, T2 after 20 minutes  $\pm$  2 minutes, T3 after 30 minutes  $\pm$  2 minutes, T4 after 40 minutes  $\pm$  5 minutes and T5 after 1 hour  $\pm$  5 minutes, T6 after 2 hours  $\pm$  5 minutes, and T7 after 4 hours  $\pm$  5 minutes.

PD effects related to craving will be assessed using a VAS scale at different timepoints. For the fixed puffing regimen the first assessment will be done 15 minutes  $\pm$  5 minutes prior to T0 fix, all other assessments will be done after T0 fix, at 4 minutes  $\pm$  2 minutes, at 10 minutes  $\pm$  2 minutes, at 15 minutes  $\pm$  2 minutes, 30 minutes  $\pm$  5 minutes, 1 hour, 2 hours, 4 hours  $\pm$  10 minutes each. For the *ad libitum* use period the first assessment will

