#### **Confidentiality Statement**

be done 15 minutes  $\pm$  5 minutes prior to T0 ad lib, all other assessments will be done after T0 ad lib, at 10 minutes  $\pm$  2 minutes, at 20 minutes  $\pm$  2 minutes, 30 minutes  $\pm$  5 minutes, 40 minutes  $\pm$  5 minutes, 1 hour, 2 hours, 4 hours  $\pm$  10 minutes each. VAS will be assessed immediately after the collection of the time-matching PK samples.

Product evaluation and sensory questionnaires will be assessed after the end of the *ad libitum* use period.

A puffing topography device will be attached to each P3P during both the fixed puffing regimen and the *ad libitum* use period. There will be one recording of HPT parameters per product use. Each P3P will be weighed before and after product use to estimate the amount of nicotine delivered in the aerosol. The number of P3P used during the *ad libitum* use period will be recorded.

In the morning of Day 2, after confirmation that there are no safety concerns for each subject to continue in the study based on Investigator's judgement, 18 subjects will be randomized in order to cross-over the use of P3P 1, P3P 2 and P3P 4.

Subjects discontinued before randomization will be replaced to reach 18 randomized subjects.

Subjects discontinued after randomization will not be replaced.

If a sufficient number of subjects are already randomized to the study sequences, any supernumerous subjects will be discontinued from the study prior to randomization only.

On Days 2, 3 and 4, subjects will be instructed to use the assigned product variant for the given study day for a fixed puffing regimen in the morning and an *ad libitum* use period in the afternoon as described for Day 1. On each study day including Day 1, start of product use should be at approximately the same time for fixed puffing in the morning and for *ad libitum* use in the afternoon with at least a 10 hour washout period between T0 fix and T0 ad lib. There will be a washout period of at least 10 hours following T0 ad lib with respect to the T0 fix of the morning of the following study day to allow adequate background correction of the nicotine plasma concentrations. The assessments performed on Days 2, 3 and 4 will be the same as those described for Day 1.

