### 12.6.5.2 Adverse Events

All AE will be listed (Listing 15.3.6.1.1) and summarized by exposure period and overall:

- The number of events and the number and percentage of subjects reporting at least one AE (Table 15.2.6.1);

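### For randomised completers the Day 4 variant, always a 2 mg one, has an adverse-event period of about 34–38 h against about 24 h for P3P 3, so by-variant AE counts are not on equal observation time

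*SAP*

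**What the plan says.** SAP 12.6.5.1 assigns each AE to an exposure period by its start time. The 1 mg variant has "P3P 3 Period: [First use of P3P 3 at Day 1, First use of product at Day 2 or time of discharge". Each 2 mg variant has the same form of definition, for example "P3P 1 Period: [First use of P3P 1, First use of the next product variant or time of discharge". AEs starting after discharge go to a separate follow-up period and are not charged to the last product used.

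SAP 12.6.5.2 then gives numbers of events and numbers and percentages of subjects, "summarized by exposure period and overall". It plans no person-time rate and no common window.

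The schedule fixes the period lengths. SAP 6.1 says that "start of product use should be at approximately the same time for fixed puffing in the morning", and the same for *ad libitum* use later in the day. It also states "There will be a washout period of at least 10 hours between T0 fix and T0 ad lib" and "There will be a washout period of at least 10 hours following T0 ad lib with respect to the T0 fix". Protocol 4.1 adds: "On Day 5, there will be no product use, but subjects will remain at the investigational site for additional PK blood sampling". The last of those samples is 24 h ± 30 min after the Day 4 T0 ad lib, and Protocol 9.4 (Table 11) places all Day 5 procedures before discharge.

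**The concern.** AE data are the primary assessment of safety (Protocol 12.6.3), and the AE tables set P3P 3 beside the three 2 mg variants. Among randomised completers only a 2 mg variant can be in use on Day 4, so only a 2 mg variant can have the long final period.

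The added hours are free of product use. They do hold the Day 5 nicotine draws, and they can hold the discharge physical examination, spirometry and ECG. An AE starting then is counted under the Day 4 variant. Events unrelated to dose could therefore look somewhat more frequent at 2 mg, and a reader of Table 15.2.6.1 could not see why. The SAP already keeps AEs from the product-free follow-up period off the last product used, but treats product-free Day 5 differently.

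**Working it through.** **The plan's own figure.** 3! = 6 sequences × 3 subjects = 18 randomised, as stated in SAP section 8. The documents give no period length in hours, so the lengths below are derived.

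**Days 1–3.** T0 fix to the next morning's T0 fix, at about the same clock time: about 24 h.

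**Day 4.** Let g be the gap from T0 fix to T0 ad lib.
- The minimum washout gives g ≥ 10 h.
- On a 24 h cycle with at least 10 h from T0 ad lib to the next T0 fix, g ≤ 24 − 10 = 14 h.
- Period to the last sample = g + 24 h, so 34 h to 38 h nominally. The ±30 min window makes this 33.5 h to 38.5 h.
- Ratio to 24 h: 34/24 = 1.42 and 38/24 = 1.58.

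Any delay between last sample and discharge adds to this.

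**Average per 2 mg variant.** In SAP Table 1, P3P 1 is on Day 4 in sequences 1 and 6, P3P 2 in 2 and 4, and P3P 4 in 3 and 5: 6 of 18 subjects each. With no dropout:
- (12 × 24 + 6 × 34)/18 = 492/18 = 27.3 h; 27.3/24 = 1.14
- (12 × 24 + 6 × 38)/18 = 516/18 = 28.7 h; 28.7/24 = 1.19

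**Effect on event counts.** Let f be the event rate after 24 h as a fraction of the rate in the first 24 h. The documents do not give f, so a range is shown. The ratio of expected counts, 2 mg variant to P3P 3, is (72 + 10f)/72 for a 34 h period and (72 + 14f)/72 for a 38 h period.

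| f | 34 h | 38 h |
|---|---|---|
| 0 | 1.00 | 1.00 |
| 0.25 | 1.035 | 1.049 |
| 0.5 | 1.069 | 1.097 |
| 1 | 1.139 | 1.194 |

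**Effect on subjects with at least one AE**, at constant hazard (f = 1) and an assumed 24 h risk p:
- p = 0.20: risk over 34 h is 1 − 0.8^(34/24) = 0.271, so the variant average is (0.20 + 0.20 + 0.271)/3 = 22.4%, and the extra subjects are 6 × 0.071 = 0.43 of 18. At 38 h: 23.3% and 0.59 subjects.
- p = 0.50: 54.2% to 55.5%, or 0.75 to 1.0 extra subjects.

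**Nicotine draws, as one exposure that is not constant in time.** A 24 h period holds 9 + 8 + 1 = 18 (the last being the next morning's pre-use sample). A Day 4 period holds 9 + 8 + 5 = 22. The 2 mg average is (18 + 18 + 22)/3 = 19.3, and 19.3/18 = 1.07: a 7% excess.

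**The case against.** Several stronger readings are tempting, and the documents do not support them.

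- *P3P 3 always has 24 h and is never charged with a discharge work-up.* Its period can also end at discharge. Exposed subjects who are never randomised exist by design (Protocol 5.2; SAP 12.2) and belong to the safety population. Their early-termination laboratory tests, ECG, spirometry and physical examination (Protocol Table 12) precede discharge. For those who stop after Day 1 use, resulting AEs fall under P3P 3.
- *The whole Day 5 work-up is extra.* The morning laboratory and urine panel, the cough assessment and a vital-signs reading have counterparts in every variant's period. Spirometry and physical-examination results are summarised by time point, not by variant, and abnormal findings become AEs only at the investigator's discretion when clinically significant (Protocol 8.4.2).
- *2 mg counts are inflated by 14–19%.* That needs a constant hazard, for which the documents give no support. Events clustered around product use would add little or nothing.
- *A planned dose comparison of AEs is biased.* The P3P 2 versus P3P 3 contrast is specified for PK and PD endpoints only; safety is descriptive. P3P 3 is also confounded with Day 1, which no change of window removes.
- *Product-event tables share the problem.* Day 5 has no product use, and Appendix A schedules no product-event recording that day.

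It is also fair to say that attributing in-clinic events to the last product until discharge is a defensible convention, and that the SAP tabulates AEs by relatedness to product and, separately, to procedures. These points limit the size. They do not remove the unequal windows from the all-causality tables, and relatedness is a judgement that does not equalise observation time.

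**Conclusion.** The point holds as a cheap improvement. For randomised completers the descriptive AE counts and percentages for P3P 3 and for the 2 mg variants rest on unequal observation time: about 24 h against an average of 27.3–28.7 h. The plan neither adjusts for this nor states it. Among completers the extra time can only add events to the 2 mg columns.

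The excess lies between 0% and about 14–19% in event counts, and is about half a subject per variant at a 20% background risk under constant hazard. These figures assume a 24 h cycle of product use, T0 ad lib 10–14 h after T0 fix, discharge at the last sample, and no dropout. Early terminators can have shorter periods. Comparisons among P3P 1, 2 and 4 are affected only if dropout is uneven.

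**What to change.** Keep the periods in SAP 12.6.5.1. In Tables 15.2.6.1 and 15.2.6.2:

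1. Add, for each variant, the AEs starting within 24 h of that day's T0 fix, or before next use or discharge if earlier.
2. Show AEs starting later, up to discharge, separately as *Day 5, no product use (after P3P x)*, still counted in the overall column.
3. Footnote the actual period lengths by variant.

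Leave Day 5 morning laboratory and cough findings with the Day 4 variant, as Protocol 12.6.3 and SAP 12.6.5.4 and 7.3.5 already arrange. This matters because the cough assessment is allowed at 24 ± 1 h after T0 fix and could otherwise fall just beyond the cut. The product-event table needs no change.

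Events per subject-hour would be a weaker remedy: dividing by hours without product use could understate the 2 mg rates.

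The cost is SAP wording and a few extra rows or columns, from times already collected. The downside is that late Day 5 events appear beside the variant's 24 h count and not inside it.

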4 INVESTIGATIONAL PLAN

4.1 Overall Study Design and Plan

This is a single-center, open-label, randomized, crossover study to evaluate the PK profiles of four P3P variants (differing in nicotine powder particle size, nicotine concentration and in the absence or presence of a flavoring system), (section 6.1), following a fixed puffing regimen and an *ad libitum* use period. In addition, PD effects (subjective effects and related behavioral assessments) as well as human puffing topography will be evaluated, to provide further insights on product acceptance and product use. Safety will also be assessed throughout the study.

Each subject will receive the four P3P variants starting with P3P 3, which has the lowest nicotine concentration, on Day 1 and continuing with P3P 1, P3P 2 and P3P 4 in a random order at the following assessment days (Figure 2). The subjects will be in confinement during the investigational period (Day -1 to Day 5).

P3P 1 characteristics: 2 mg nicotine; 2.25 μ m nicotine powder particle size; unflavored

P3P 2 characteristics: 2 mg nicotine; 2.25 μ m nicotine powder particle size; flavored

P3P 3 characteristics: 1 mg nicotine; 2.25 μ m nicotine powder particle size; flavored

P3P 4 characteristics: 2 mg nicotine; 1.8 μ m nicotine powder particle size; flavored

Figure 2 Study Flow Chart

The Screening Visit (Day -22 to Day -2)

A Screening Visit will be conducted within 3 weeks prior to Admission to the investigational site. Eligibility criteria will be verified at the Screening Visit (section 5.1). A demonstration of P3P (without product use) will be done by the investigational site staff.

The Admission Visit (Day -1)

Subjects will return to the investigational site for Admission (Day -1). Subjects should have been fasting for at least 6 hours prior to Admission. After confirmation of eligibility, subjects will be enrolled. All subjects that are not enrolled will be considered as screen failures. At

Confidentiality Statement

Data and information contained in this document are considered to constitute trade secrets and confidential commercial information, and the legal protections provided to such trade secrets and confidential information are hereby claimed under the provisions of applicable law. No part of this document may be publicly disclosed without the written consent of Philip Morris Products S.A.

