6.2.2 Investigational Period (Day 1 to Day 5)

Each subject will use P3P 3 on Day 1. In the morning of Day 2, subjects will be randomized to one of six sequences in order to cross-over to the use of P3P 1, P3P 2 and P3P 4 on Days 2, 3 and 4 (section 6.3).

On each assessment day (Day 1 to Day 4), following at least 10 hours of abstinence from any tobacco and nicotine containing products, subjects will use the assigned product for the given visit with two product use regimen as described in Figure 2:

- using a fixed puffing regimen comprising of 12 puffs in total at a rate of one inhalation every 30 seconds (\pm 5 seconds) in the morning.
- using *ad libitum* use period for 60 minutes (\pm 5 minutes) in the afternoon.

A puffing topography device will be attached to each P3P. There will be one recording of HPT parameters per product. Each P3P product will be weighed before and after product use to estimate the amount of nicotine delivered in the aerosol. During the *ad libitum* use period, the subjects can use the product according to their puffing behavior, without restrictions in the number of puffs, interpuff interval duration or number of products used. The number of P3P products used during the *ad libitum* use period will be recorded. The start and stop time of each product used during each puffing regimen will be recorded as well as the total number of puffs taken at the fixed puffing regimen.

The start of product use for fixed puffing and for the *ad libitum* use period will be defined as T_0 fix and T_0 ad lib, respectively. There will be a washout period of 10 hours between T_0 fix and T_0 ad lib.

There will be no product use on the Discharge day (Day 5).

Except for the assigned products, subjects will not be allowed to use any nicotine-containing products through Discharge or early termination.

Subjects will be continuously supervised by the investigational site staff during P3P use.

Confidentiality Statement

Data and information contained in this document are considered to constitute trade secrets and confidential commercial information, and the legal protections provided to such trade secrets and confidential information are hereby claimed under the provisions of applicable law. No part of this document may be publicly disclosed without the written consent of Philip Morris Products S.A.

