8.2 Collection and Reporting of Adverse Events

8.2.1 Collection of Information

Any non-serious AE occurrence during the study must be documented in the subject's medical records in accordance with the Investigator's normal clinical practice and on the AE page of the CRF. SAEs that occur during the study must be documented in the subject's medical record, on the AE CRF, and on the SAE form.

AEs should be collected mainly via face-to-face interview with the subject through spontaneous reporting or by the use of consistent, open, non-directive questions from the investigator(s) or designee(s) (e.g., "Have you had any health problems since you were last asked? or "How have you been feeling since you were last asked?").

Information recorded will include: verbatim description of the AE/SAE, start and stop dates, seriousness, severity (intensity), action taken (e.g., whether or not the AE/SAE led to the subject's discontinuation from the study), and outcome (e.g., resolved, stabilized).

Information to be recorded about an AE/SAE should include, whenever possible, onset and resolution dates and times, circumstances leading up to the event, clinical elements such as clinical course, specific vital signs and test results that may explain the pathophysiology of the event, as well as alternative explanations to its occurrence.

Whenever a medically meaningful diagnosis is available to comprise a set of reported signs and/or symptoms, it should be preferentially provided as the AE or SAE term, rather than the individual signs and/or symptoms. Otherwise, each one of those signs and/or symptoms should be reported separately as event terms.

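### Adverse events are placed in an exposure period by start time alone, so a worsened pre-dose event has no variant column and later worsening can be shown under P3P 3

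*SAP*

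**What the plan says.** SAP 12.6.5.1 splits each subject's time into seven consecutive periods: pre-dose, product test, one for each of the four variants, and safety follow-up. The P3P 3 window, for example, is "P3P 3 Period: [First use of P3P 3 at Day 1, First use of product at Day 2 or time of discharge", with the end point excluded. The assignment rule is "Safety data will be assigned to the specific safety period where the collection time or start time of the AE is included", meaning that it falls within the limits of that period. Start time is the part that applies to AEs; collection time serves the other safety data.

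The same section counts as product-emergent any AE that arises after the first P3P use, and also one that is "present prior to first product use and becomes more severe after first product use". Only product-emergent AEs are summarized, and the sentence saying so adds that "the ones occurring during pre-dose period will be listed only".

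SAP 12.6.5.2 then tabulates AEs by exposure period and overall. The rows include severity (each subject once, at the worst grade), action taken, and AEs leading to product or study discontinuation.

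For each AE, Protocol 8.2.1 asks for "start and stop dates, seriousness, severity (intensity), action taken" and outcome, together with a verbatim description. The date or time of a change in severity is not among the required items.

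On order of use, Protocol 4.1 says: "Each subject will receive the four P3P variants starting with P3P 3".

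**The concern.** Protocol 12.6.3 makes AE data the primary safety assessment and has them summarized by variant. The tables should therefore show what happened under each variant. A rule based on start time alone can fail in two ways.

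- **Pre-dose AEs that worsen.** The SAP gives two instructions for the same event: summarize it, because it is product-emergent, and only list it, because it began pre-dose. Two programmers could reasonably produce different tables.
- **AEs that worsen from one variant to the next.** Whether an AE is emergent is decided once, at the Day -1 product test. Nothing asks the question again at the first use of each variant. An event that is mild on the 1 mg product and becomes severe on a 2 mg product could appear as a severe P3P 3 event, with any resulting discontinuation beside it. The 2 mg column would show nothing.

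The second failure bears on the comparison between nicotine contents, because the fixed order means that randomization cannot balance it.

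**Working it through.** The plan states no figure to reproduce here. The check applies the SAP 12.6.5.1 rule literally to test events, looks for a rule elsewhere that closes the gap, counts the order of use, and sizes one subject.

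**1. Test events, each kept as one record.**

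| Event | Product-emergent by the SAP definition | Period by start time | Period of worsening |
|---|---|---|---|
| Starts pre-dose, worsens Day 1 | Yes | Pre-dose (listed only) | P3P 3 |
| Starts pre-dose, worsens Day 2 | Yes | Pre-dose (listed only) | Day 2 variant |
| Starts after the product test, worsens Day 2 | Yes | Product Test | Day 2 variant |
| Starts Day 1, worsens Day 2 | Yes | P3P 3 | Day 2 variant |
| Starts Day 2, worsens Day 3 | Yes | Day 2 variant | Day 3 variant |

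The first two rows are the contradiction. Nothing says whether such an event enters the overall column. The other rows are the gap: in each, the period of worsening receives no count.

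**2. Does another rule close the gap?**

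- Protocol 8.1.3 requires a worsened condition to be captured as an AE, but only a condition that existed before consent was signed.
- Protocol 12.6.3 assigns laboratory AEs to the product of the previous day. It covers laboratory AEs only.
- SAP 12.6.5.2 counts a subject once per preferred term for each sequence, at the worst occurrence. That concerns repeated occurrences, and the tables are by exposure period.
- SAP Table 18 handles partial dates by month and year, not worsening.

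None of these re-counts an AE that worsens in a later period.

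**3. Direction.** The six sequences for Days 2 to 4 (Protocol Table 2, SAP Table 1) are 2-4-1, 4-1-2, 1-2-4, 1-4-2, 2-1-4 and 4-2-1. All follow P3P 3 on Day 1.

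- P3P 3 precedes each of P3P 1, 2 and 4 in 6 of 6 sequences.
- Each of P3P 1, 2 and 4 precedes each of the others in 3 of 6.

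For events that start in the P3P 3 period, the misattribution can only go from a later variant to P3P 3. Among the three 2 mg variants it is balanced by design.

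**4. Size of one subject.** With 6 × 3 = 18 subjects in a column, one subject is 1/18 = 5.56%. This is an assumption, since no column denominator is stated. Subjects who leave before randomization are replaced, so the safety population may exceed 18: 1/19 = 5.26% and 1/20 = 5.00%. SAP 12.6.5.2 calls an event frequent above 5% of the safety population. One subject therefore passes that threshold at 18 or 19 but not at 20.

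**The case against.** The strongest reply has five parts.

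1. **An AE that starts under P3P 3 is a P3P 3 event.** This stands. A reader might infer that the rule makes the 1 mg product look worse in incidence, with each affected subject moving 5.6 points from a 2 mg variant to P3P 3 and two subjects creating an 11-point difference (2/18 = 11.1%). The documents do not support that. The onset belongs in P3P 3 under any sensible rule, so nothing moves. What is missing is a count under the later variant. Two subjects may also worsen under different variants, and a subject adds to the row for at least one AE only if no other AE is already counted there.
2. **Day -1 onsets do not reach P3P 3.** This also stands, because Product Test is a separate column.
3. **Recording practice is not visible.** It is governed by the CRF and its completion guidelines. If the site opens a new record at each worsening, the start-time rule puts that record under the later variant. Protocol 8.2.1 also asks, where possible, for onset and resolution times and clinical course. So the second problem is conditional on single records. Neither document requires a new record, however.
4. **Worsened pre-dose AEs may not be lost.** A reader might infer that the SAP certainly drops them. The listed-only remark can be read as describing ordinary pre-dose events, and an overall column exists. What is established is a contradiction and no assigned variant column, not a proven exclusion.
5. **Related symptoms are measured elsewhere.** Cough is assessed about 24 hours after each variant's fixed-regimen start, dizziness and nausea are in the adapted mCEQ, and harshness is in the sensory questionnaire. That helps interpretation for those symptoms, but it does not correct the AE tables and does not show action taken or discontinuation.

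The study also tests no hypothesis and makes no claim from individual intervals. That limits the consequence to the descriptive safety tables.

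**Conclusion.** The point holds in two parts of different strength.

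The contradiction in SAP 12.6.5.1 follows from the text alone. A pre-dose AE that worsens after first use is both to be summarized and to be listed only, and it has no variant column.

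The misattribution between variants holds if a worsening AE is kept as one record. The later worst severity, action taken and any discontinuation then appear in the period of onset, and the later variant shows nothing. This is one-directional for P3P 3 against P3P 1, 2 and 4, and balanced among those three. P3P 3 onset incidence is right as it stands.

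One subject amounts to about 5.6 percentage points of a column, given a denominator of 18 and no other AE for that subject in that column. The documents do not say how many subjects would be affected. No inferential result is touched.

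**What to change.** Amend SAP 12.6.5.1 as follows:

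- Assign an AE to the period of onset, with the severity reached in that period.
- Where the record or source gives the time of worsening, also count the AE as product-emergent in the period of worsening, with the severity reached there.
- Exempt pre-dose AEs that worsen after first use from the listed-only rule, and assign them to the period of worsening.
- Attribute action taken and discontinuation to the period in which they occurred.

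If data collection is still open, have each worsening recorded with its date and time. It may not be: the CRF was final in August 2017, and SAP version 2.0 followed review of draft interim PK results. In that case, identify the affected AEs at the pre-analysis data review meeting (SAP 13.5) and flag those with no worsening time.

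The cost is SAP wording, a little programming and a short record review, with no new assessment. SAP section 3 allows amendment until database lock. The downside is that event counts will include worsenings as well as onsets, which a table footnote should state.
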